Patient Population and Key Selection Criteria	Male and female patients, aged $\geq 18$ years, who received at least 2 Ozurdex implant in the same eye to treat visual impairment due to DME. Among these patients, sites will also be requested to do their best to select a subgroup of up to 50 patients that are naïve to anti-VEGF treatment prior to first Ozurdex implant injection. Patients may contribute at most one eye into the study. If both eyes meet the inclusion criteria, the eye that received the most Ozurdex injections will be chosen as the study eye.
Sample Size	The study aims to select 150 patients. As study primary objective is to assess reinjection interval in real-world, sample size calculation were performed to evaluate the precision around the mean of the reinjection interval.  Considering standard deviations ranging from 1.5 to 3, the selection of 150 patients will enable the description of a mean reinjection interval with satisfactory precisions (half of the 95% confidence interval) ranging from 0.2 to 0.5 months, i.e. from 6 to 15 days (worst case).
Outcome Variables and Assessments	
Ozurdex Real-word Utilization
 
 
Number of Ozurdex implant injections per year
 
Time between Ozurdex implants injections
 
 
Effectiveness:
 
 
Best-corrected visual acuity (BCVA) change from time of injection to 7–12 weeks following each Ozurdex implant injection
 
BCVA change from time of first Ozurdex implant injection to 7–12 weeks following each Ozurdex implant injection
 
Central retinal thickness (CRT) by optical coherence tomography (OCT) change from time of injection to 7–12 weeks following each Ozurdex implant injection
 
CRT by OCT change from time of first Ozurdex implant injection to 7–12 weeks following each Ozurdex implant injection
 
 
Safety:
 
 
Number and percentage of patients who experienced AESIs
 
[REDACTED]
 
[REDACTED]
 

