## 7 STUDY CONDUCT

### 7.1 Overall Design of the Study

This is a retrospective, non-interventional, observational, multi-center, drug utilization study to be conducted in adult patients with visual impairment due to DME treated with Ozurdex implants in Germany and Switzerland from 1 January 2015 to 1 September 2018. Data from approximately 150 patients will be collected by retrospective review of medical charts; including up to 50 patients that are naïve of any anti-VEGF treatment before their first Ozurdex implant injection. Sites will be hospital-based experienced medical retina centers treating DME patients.

Patients' medical charts will be selected over a 4-month period at each site or until the study target population has been reached. Site personnel will be invited to complete a screening log with all patients who received at least one Ozurdex implant injection after the 1 January 2015 to help them identify eligible patients. For each patient, retrospective data on the study eye will be abstracted from existing medical records from time of first Ozurdex implant injection until 1 September 2018. Data abstraction will cover at least one year of follow-up after first Ozurdex injection for all selected patients. The study eye will be defined as the eye that received the most Ozurdex injections. Key relevant data will also be collected on the contralateral eye.

Study procedures, and evaluations are described in detail in Sections 9 to 11 and data to be collected are summarized in Table 2. Safety events to be collected are described in Section 10.9.

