## 14 STATISTICAL METHODS

### 14.1 Sample Size

The study aims to select 150 patients. As study primary objective is to assess reinjection interval of Ozurdex implant in real-world, sample size calculations were performed to evaluate the precision around the mean of the reinjection interval.

Few data were published on the reinjection interval in patients diagnosed with diabetic macular edema in real-world. Matropasqua et al. reported a mean  $\pm$  standard deviation (SD) of  $6.7 \pm 2.3$  months in 27 Italian patients. Querques et al. reported a mean of 4.9 and 4.7 months from respectively 570 French patients of a pharmacist database and 114 patients from the French Social Security database (no standard deviations were available). The same study also reported a mean ( $\pm$ SD) of  $4.8 \pm 1.8$  months between reinjections based on data from 111 French ophthalmologists who completed a survey about their practice.

The precision of the 95% confidence interval (CI) of the mean ( $\omega$ , half of the width of the CI) is determined using the following formula:

$$\omega = \frac{1.96 \times SD}{\sqrt{n}}, \text{ where SD is the standard deviation and } n \text{ is the sample size.}$$

Table 4 shows the precision and 95% CI of the mean considering a SD ranging from 1.5 to 3.0 and a sample size of 150 patients.

**Table 4 Precision and 95% CI of the mean considering a standard deviation ranging from 1.5 to 3.0, a mean ranging from 4.7 to 6.7 and a sample size of 150 patients**

SD	Mean (month)				
	$\omega$	4.7	5.5	6.0	6.7
1.5	0.2	4.5-4.9	5.3-5.7	5.8-6.2	6.5-6.9
2.0	0.3	4.4-5.0	5.2-5.8	5.7-6.3	6.4-7.0
2.5	0.4	4.3-5.1	5.1-5.9	5.6-6.4	6.3-7.1
3.0	0.5	4.2-5.2	5.0-6.0	5.5-6.5	6.2-7.2

Considering SD of the mean reinjection interval ranging from 1.5 to 3 months, the selection of 150 patients will enable the description of a mean reinjection interval with precision ranging from 0.2 to 0.5 months, i.e. 6 to 15 days (worst case).

For example, for a mean interval between two Ozurdex injections of 6.0 months, the 95% CI of the mean would be 6.0 [5.5-6.5] months in the worst case (i.e., 183 days [168-198],  $\omega = 15$  days).

 Standard deviation was not clearly available in the paper and was recalculated from available data.

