A secondary objective of the study is to assess drug effectiveness in a subgroup of patients who are naïve of any anti-VEGF treatment. One of the outcomes of interest for this subgroup of patients will be the change in BCVA from the first injection to 7-12 weeks following each reinjection.

In 2015 Escobar-Barranco et al reported a difference in visual acuity from baseline to 6 months (mean  $\pm$  SD) of  $11.5 \pm 4.6$  ETDRS letters in 36 treatment naïve patients whereas in 2018 Iglicki et al. reported a gain at 24 months (mean  $\pm$  SD) of  $11.3 \pm 10.0$  letters in 71 eyes of treatment naïve patients.

The precision and 95% CI of the mean have been calculated considering a mean gain of 11.5 letters, standard deviation ranging from 4.5 to 10.0 and a sample size of 50 patients (Table 5).

**Table 5 Precision and 95% CI of the mean considering a mean gain of 11.5 letters, a standard deviation ranging from 4.5 to 10.0 and a sample size of 50 patients**

SD	$\omega$	95% CI
4.5	1.3	10.2-12.8
6.0	1.7	9.8-13.2
8.0	2.2	9.3-13.7
10.0	2.8	8.7-14.3

Considering SD ranging from 4.5 to 10.0, a subgroup of 50 patients who are treatment naïve will enable to describe a mean change in visual acuity with precision ranging from 1.3 to 2.8. For example, for a mean change in visual acuity of 11.5, the 95%CI of the mean will be 11.5 [8.7-14.3] letters in the worst case. It has been considered as satisfactory for this secondary objective.

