In 2015 Escobar-Barranco et al. reported a difference in visual acuity from baseline to 6 months (mean  $\pm$  SD) of  $11.5 \pm 4.6$  ETDRS letters in 36 treatment naïve patients whereas in 2018 Iglicki et al. reported a gain at 24 months (mean  $\pm$  SD) of  $11.3 \pm 10.0$  letters in 71 eyes of treatment naïve patients.

The precision and 95% CI of the mean have been calculated considering a mean gain of 11.5 letters, a standard deviation ranging from 4.5 to 10.0 and a sample size of 50 patients (Table 18-2).

**Table 18-2 Precision ( $\omega$ ) and 95% CI of the mean considering a mean gain of 11.5 letters, a standard deviation ranging from 4.5 to 10.0 and a sample size of 50 patients**

SD	$\omega$	95% CI
4.5	1.3	10.2-12.8
6.0	1.7	9.8-13.2
8.0	2.2	9.3-13.7
10.0	2.8	8.7-14.3

Considering SD ranging from 4.5 to 10.0, a subgroup of 50 patients who are treatment naïve will enable to describe a mean change in visual acuity with precision ranging from 1.3 to 2.8. For example, for a mean change in visual acuity of 11.5 letters, the 95% CI of the mean will be 11.5 [8.7-14.3] letters in the worst case. It has been considered as satisfactory for this secondary objective.

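### The 2.8-letter worst-case precision for anti-VEGF-naive patients varies only the SD; it treats a recruitment target of up to 50 as the evaluable number for an outcome analysed after each reinjection

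*Protocol*

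**What the plan says.** Protocol 14.1 names an outcome of interest for the naive subgroup: "the change in BCVA from the first injection to 7-12 weeks following each reinjection". It then computes the half-width of the 95% CI "considering a mean gain of 11.5 letters, standard deviation ranging from 4.5 to 10.0 and a sample size of 50 patients" (Table 5). At the largest SD it reports that "the 95%CI of the mean will be 11.5 [8.7-14.3] letters in the worst case" and calls this satisfactory for the secondary objective. SAP 19.0 repeats the calculation (Table 18-2) and the conclusion: "the 95% CI of the mean will be 11.5 [8.7-14.3] letters in the worst case".

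Elsewhere the same 50 is a ceiling reached by best effort. Protocol 7.1 describes about 150 patients, "including up to 50 patients that are naïve of any anti-VEGF treatment". The Protocol synopsis says that "sites will also be requested to do their best to select a subgroup of up to 50 patients". Protocol 9.2 stops naive recruitment at about 50.

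Protocol 14.2.2.3.3 and SAP 15.2.3 (through 15.2.1) analyse the outcome separately for each reinjection. Protocol 8.2.1 requires at least two implants in the study eye and at least 12 months of follow-up counted from the first one.

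**The concern.** A precision statement holds for the number of patients who enter the mean. Here that number is the naive patients who received the reinjection in question and have a BCVA in the window after it. The plan substitutes the recruitment target and varies only the SD, so the label worst case covers one of the two quantities that set the half-width.

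Several features of the plan can bring the evaluable number below 50:

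- Recruitment of naive patients may fall short of the target.
- No second or later reinjection is required for eligibility.
- Follow-up may be as short as 12 months from the first implant, and no minimum is set after the second.
- The minimum dataset (Protocol 8.2.4) asks for a BCVA after each implant but does not tie it to the window.
- Protocol 7.3.2 expects gaps in the charts and rules out queries.
- SAP 21.2 ends follow-up at the first concomitant anti-VEGF or corticosteroid, and SAP 15.2.1 describes BCVA during the follow-up period.

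Section 14.1 allows for none of these. At stake is what readers are told to expect: this is the only precision figure offered for the naive subgroup, which serves a named secondary objective.

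**Working it through.** **Inputs.** From Protocol 14.1 (same in SAP 19.0): half-width ω = 1.96 × SD / √n, mean gain 11.5 letters, SD 4.5 to 10.0, n = 50.

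**Reproducing the plan's figure.** ω = 1.96 × 10 / √50 = 2.77, rounded to 2.8; interval 11.5 ± 2.77 = 8.7 to 14.3. A t quantile with 49 degrees of freedom gives 2.84, also 2.8. The stated figure is correct for its inputs.

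**Margin at SD 10.** n = 49 gives 19.6 / 7 = 2.80; n = 48 gives 2.83, which still rounds to 2.8; n = 47 gives 2.86, which rounds to 2.9. Below 48 evaluable patients the printed 2.8 no longer holds.

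**Smaller evaluable n at SD 10.** These n are assumptions; the documents give no evaluability rate.

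| Evaluable n | ω (letters) | 95% CI around 11.5 |
|---|---|---|
| 50 | 2.8 | 8.7-14.3 |
| 40 | 3.1 | 8.4-14.6 |
| 30 | 3.6 | 7.9-15.1 |
| 20 | 4.4 | 7.1-15.9 |

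**Smaller SDs.** The n needed for ω ≤ 2.8 is (1.96 × SD / 2.8)² rounded up: SD 8 gives 31.4, so 32; SD 6 gives 17.6, so 18; SD 4.5 gives 9.9, so 10.

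**Why later reinjections have fewer patients.** Table 4 uses mean intervals of 4.7 to 6.7 months. Two such intervals put the second reinjection at 9.4 to 13.4 months after the first implant, and three put the third at 14.1 to 20.1 months, before the assessment window opens. A patient with the minimum 12 months of follow-up may not reach them.

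**Illustration by reinjection.** Assume 50 recruited, all with a BCVA in the window, SD 10, and a constant proportion going on from each reinjection to the next. The 66% borrows the only such proportion in the documents (Protocol 5.1, 27 treatment-naive patients). That figure concerns a first reinjection within one year, so it only marks a range here.

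| Proportion going on | n at reinjections 1 / 2 / 3 / 4 | ω |
|---|---|---|
| 90% | 50 / 45 / 40 / 36 | 2.8 / 2.9 / 3.1 / 3.3 |
| 80% | 50 / 40 / 32 / 26 | 2.8 / 3.1 / 3.5 / 3.8 |
| 66% | 50 / 33 / 22 / 14 | 2.8 / 3.4 / 4.2 / 5.2 |

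If only 80% have a BCVA in the window (again an assumption), the first reinjection already has n = 50 × 0.8 = 40 and ω = 3.1.

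**A separate small point in the same table.** The SD 4.5 row prints 1.3, but 1.96 × 4.5 / √50 = 1.25 (1.247 unrounded), which rounds to 1.2. This does not affect the 2.8.

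**The case against.** The strongest reply is that the plan states its condition openly. The sample size of 50 stands in the table title and the text, and worst case plainly means the top of the SD range, as in the primary-objective calculation. Nowhere does the plan claim 50 evaluable patients at every reinjection; that is an inference from the outcome definition together with the single n. This stands, and there is no arithmetic error in the 2.8.

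It also stands that numbers do not fall through non-receipt at the first reinjection, because two implants are an inclusion criterion. SAP 21.2 widens the window by two weeks on each side, to Days 35 to 98, which limits losses from visit timing. The study has no hypothesis, the naive comparison is descriptive without tests (SAP 15.2.3), and missing counts will be reported (SAP 21.1), so readers of the results will see the actual n.

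A reader might go further and infer that the design cannot deliver 2.8, or that 50 is the best case. The documents support neither. If 50 are recruited and all are evaluable, 2.8 is reached at the first reinjection even at SD 10, and smaller SDs in the stated range keep it with 10 to 32 patients. The analysed subgroup could also exceed 50: the roughly 100 consecutively selected patients in Protocol 9.2 are not described as non-naive in the readable text, and SAP 6.3 and 21.3.1 derive naive status from the eCRF. Part of the selection text is redacted.

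None of this makes 2.8 a worst case for an outcome summarised after each reinjection.

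**Conclusion.** The point holds as a misstated precision claim. The half-width of 2.8 letters is correct for SD 10 and n = 50, but it is worst only over the SD and carries almost no margin in n: at SD 10 it is exceeded, after rounding, below 48 evaluable patients. The design does not guarantee it at the first reinjection when the SD is 10, and it should not be expected at later reinjections, for which eligibility secures no patients.

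The actual loss cannot be computed from the documents. Over an assumed range of 40 down to 20 evaluable patients at SD 10 the half-width is 3.1 to 4.4 letters, about 1.1 to 1.6 times the stated figure (3.1 / 2.8 and 4.4 / 2.8). No test, decision or primary result depends on it. The consequence is confined to the stated expectation for a descriptive secondary objective.

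**What to change.** In Protocol Table 5 and SAP Table 18-2, add half-widths at SD 10 for smaller evaluable n: 40 (3.1; 8.4-14.6), 30 (3.6; 7.9-15.1) and 20 (4.4; 7.1-15.9). Label them as illustrative assumptions, since no evaluability rate is available.

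In the text of both documents, replace the worst-case wording by the condition: *at SD 10, if 50 naive patients are recruited and all have a BCVA in the window*. Add that this applies at most to the first reinjection and that wider intervals are expected at later ones. The half-width in the SD 4.5 row can be brought into line with the stated formula in the same edit.

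The cost is text and two tables. No design feature, analysis or data collection changes; the stated precision becomes less favourable.

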## 14.2 Study Populations and Analyses

A formal SAP that will provide details of all analyses and presentation of study data will be approved prior to data analysis. Statistical analysis will be carried out using SAS software version 9.2 or later.

### 14.2.1 Study Populations and Analysis Methods

- Analysis Population: data will be summarized for all patients who were selected and met the selection criteria.
- Subgroups analysis will be conducted in patients who are naïve for anti-VEGF treatment. If the sample size allows it, analyses will also be conducted in a subgroup of patients who received 6 or less anti-VEGF treatments prior to the first Ozurdex implant injection.
- Additional groups also may be examined, as deemed appropriate such as according to lens status at baseline (phakic vs. pseudophakic) or according to concomitant treatments (concomitant anti-VEGFs vs. Ozurdex only).

Continuous variables will be described by their mean, SD, median, first and third quartiles, extreme values (minimum and maximum) and the number of missing data.

Categorical variables will be described by the total and percentage of each response and the number of missing data.

Two-sided 95% CI of the mean and of percentage may also be calculated when appropriate. Data may also be presented graphically when relevant.

## **14.2.2Planned Analyses**

### **14.2.2.1 Disposition and Patients' Characteristics**

Disposition of patients in the Analysis Population and number of study and contralateral eyes for which data are available will be described.

Clinical examinations, prior and concomitant treatments, and contralateral eye data will be summarized descriptively.

### **14.2.2.2 Primary Objective**

Number of patients with at least one reinjection and number of reinjections per patient during the year following the first Ozurdex implant injection will be summarized descriptively for all patients from the Analysis population. For patients with more than one year of follow-up, number of patients with at least one reinjection and number of reinjections per patient during the follow-up year considered will be described for each year of follow-up (e.g. 2nd year of follow-up, 3rd year of follow-up...). The number and percentage of patients receiving each injection (first, second, etc.) will be presented for each year of follow-up.

Time between Ozurdex implant injections will be summarized overall and for each reinjection, i.e. first reinjection, second reinjection...

### **14.2.2.3 Secondary Objectives**

[figure not shown]
#### **14.2.2.3.1 Relationship between Re[in]jection Intervals and Effectiveness**

Analysis will be performed considering each Ozurdex reinjection separately (second injection or first reinjection, third injection or second reinjection...) (see Figure 1).

Change in BCVA from time of reinjection to 7-12 weeks following reinjection and change in BCVA from time of first injection to 7-12 weeks following reinjection will be summarized for each reinjection. The same analyses will be performed for the change in CRT.

A first approach to assess the relationship between reinjections intervals and effectiveness will be to consider time interval between two injections (previous injection - reinjection) as a continuous parameter. The potential relationship between time interval and effectiveness will be assessed graphically using a scatter plot. Time interval between two injections (in months) will be plotted on the horizontal axis and either BCVA change or CRT change from time of reinjection to 7-12 weeks following reinjection will be plotted on the vertical axis. The corresponding correlation coefficients will be calculated. The same scatter plot will be done for the change in BCVA and CRT from time of first implant injection to 7-12 weeks following each Ozurdex implant injection.

**Figure 1 Example of Reinjections Intervals and Effectiveness Outcomes Disposition in a Hypothetic Patient**

BCVA=Best corrected visual acuity; CRT=Central retinal thickness

- Last BCVA and CRT measured before injection of Ozurdex
- BCVA and CRT measured 7 to 12 weeks following each reinjection

For "Time interval 1", BCVA and CRT change from measurement 1 to measurement 2 will be considered; for "Time interval 2" BCVA and CRT change from measurement 3 to measurement 4 will be considered; and for "Time interval 3", BCVA and CRT change from measurement 5 to measurement 6 will be considered.

A second approach will be to consider time interval between two injections as a categorical variable; either 2 categories will be considered based on median time interval or other categories will be considered based on observed distribution. BCVA change and CRT change from reinjection to 7-12 weeks following reinjection and BCVA and CRT change from time of first implant injection to 7-12 weeks following each Ozurdex implant injection will be described by these categories.

#### 14.2.2.3.2 Reason for Ozurdex Implant Initial Injection and for Reinjection

Reason for initial injection and for reinjection of Ozurdex implants will be summarized descriptively.

#### 14.2.2.3.3 Drug Effectiveness in Patients Naïve of any Anti-VEGF Treatment

Change in BCVA from time of reinjection to 7-12 weeks following reinjection and change in BCVA from time of first injection to 7-12 weeks following reinjection will be summarized for each reinjection considering the subgroup of patients who are treatment naïve of any anti-VEGF treatment. The same will be performed for the change in CRT.

#### 14.2.2.3.4 Adverse Events of Special Interest

Adverse events of special interest (AESIs) potentially related to Ozurdex reinjection will be summarized descriptively. Number and percentage of patients who experienced AESIs

will be described overall [REDACTED]. [REDACTED]

## 15 ETHICAL CONDUCT OF THE STUDY

### 15.1 Ethics Statement

The study shall be conducted in compliance with International Society for Pharmacoeconomics and Outcomes Research (ISPOR) Good Pharmacoeconomics and Outcomes Research Practice (GPP) guidelines, the ethical principles arising from the Declaration of Helsinki revised in 2013, the European Union Good Pharmacovigilance practices (GVP), European and National laws in terms of data protection and all current local regulations. Relevant scientific guidelines such as ENCePP Guide on Methodological Standards in Pharmacoeconomics will be considered.

### 15.2 Informed Consent

Due to the retrospective and anonymous nature of data collection for this study, signature of informed consent by patients is not required to abstract data from the patient's chart. A waiver of consent will be requested from IECs.

### 15.3 Institutional Review Board / Independent Ethics Committee Approval

This study is non-interventional. The drug used to treat the patient is based on clinical judgment alone, and, as such, does not come under applicable laws and regulation on clinical trials, as no drug is provided by the Sponsor or any third party. No specific examinations or laboratory tests are to be performed above and beyond those usually undertaken by the investigator, and no additional visits are required for study purposes.

Submissions and/or notification to the appropriate IEC will be performed as required by local legislation in each country for this type of study.

### 15.4 Data Protection

Patients' personal data and investigator's personal data shall be treated in compliance with the European Regulation on the protection of individuals with regard to the processing of personal data and all local applicable laws and regulations.

Data about investigators will be declared to applicable data protection authority and the investigators will be informed – within the framework of the site qualification questionnaire – of their right to access to, rectify or erase data, or their right to restrict or object to processing of the data, as well as the right to data portability.

Patient data will be anonymized, i.e. investigators will not be able to connect the patient with his/her identification number. The sponsor will be blinded to the patient information.

Submission(s) to competent data protection authorities will be performed as appropriate.

